8.2 Background Characteristics

8.2.1 Subject Disposition

The number of subjects in the following categories will be summarized overall and by study arm:

- Randomized
- Safety Set
- Full Analysis Set (FAS)

The number and percentage (based on FAS) of subjects in each of the following disposition categories will be summarized overall and by study arm:

- Completed study drug
- Prematurely discontinued study drug and the reason for discontinuation
- Completed study (defined as completed the planned study treatment and Safety Follow-up Visit)
- Prematurely discontinued the study and the reason for discontinuation

A listing will be provided for subjects who discontinued treatment or who discontinued study, along with reasons for discontinuations.

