### 8.1.3 Follow-up

Subjects will have a Safety Follow-up Visit 28 ( $\pm$  7) days after the last dose of LUM/IVA. Safety Follow-up Visit assessments are listed in [Table 3-2](#). Subjects who begin commercial LUM/IVA before this visit do not have to complete the Safety Follow-up Visit.

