### **12.3.2      Background Characteristics**

#### **12.3.2.1    Subject Disposition**

The number and percentage of subjects in each disposition category (e.g., randomized, included in the FAS, included in the Safety Set, completed study/Safety Follow-up Visit, and discontinued use of smart adherence technology or study with a breakdown of the reasons for discontinuation) will be summarized overall and by study arms.

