### **13.1.1.3 Documentation of Adverse Events**

All AEs will be collected from the time the ICF is signed until the following time points:

- For subjects who do not enroll: until time of screen failure (e.g., screen failure, withdrawal of consent)
- For enrolled subjects who have a Safety Follow-up Visit: through the Safety Follow-up Visit
- For enrolled subjects who do not have a Safety Follow-up Visit, the **earliest** of:
  - 28 days after the last dose of LUM/IVA or
  - Dosing with commercial LUM/IVA

All subjects will be queried, using non-leading questions, about the occurrence of AEs at each study visit. When possible, a constellation of signs and/or symptoms will be identified as 1 overall event or diagnosis. All AEs for enrolled subjects will be recorded in the eCRF and source document. AEs for subjects who are screened but not subsequently enrolled in the study will be recorded only in the subject's source documents. The following data will be documented for each AE:

- Description of the event
- Classification of “serious” or “nonserious”
- Date of first occurrence and date of resolution (if applicable)
- Severity
- Causal relationship to LUM/IVA(s)
- Action taken
- Outcome
- Concomitant medication or other treatment given

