6 STUDY DESIGN

This is a Phase 4, open-label, randomized, multicenter, 2-arm, parallel-group pilot study evaluating LUM/IVA adherence. Each study arm will use a smart technology with either active or inactive dosing alert features.

This study includes:

- Screening Period (Day -28 through Day -1)
- Treatment Period (Day 1 through Week 48)
- Safety Follow-Up Visit (28 [± 7] days after the final dose of study drug). Subjects who begin commercially available LUM/IVA combination therapy within 28 (± 7) days of the last dose of LUM/IVA do not have to complete the Safety Follow-up Visit.

[Figure6-1](#) depicts a schematic of the study design. Approximately 75 subjects will be enrolled in this study. All subjects will receive LUM 400 mg/IVA 250 mg every 12 hours (q12h) through Week 48.

[figure not shown]
Randomization of subjects to the 2 study arms will be stratified by age (<23 versus ≥ 23 years of age) and forced expiratory volume in 1 second (FEV₁) severity ($<70\%$ versus $\geq 70\%$ predicted) at the Screening Visit. All subjects will be randomized at 2:1 ratio to 1 of the following 2 smart adherence technology study arms:

- **Study Arm A:** Smart Pill Bottle, activated
- **Study Arm B:** Smart Pill Bottle (control), de-activated alerts and feedback features

Subjects will receive standardized education on the benefit of medication adherence and training on the use of the assigned smart adherence technology. During applicable study visits, subjects will complete adherence and technology satisfaction assessments; and physicians will complete technology satisfaction assessments at Week 48. Tables 11-1 and 11-2 in Appendix A provide a list of assessments by study visit.

All subjects will be required to complete study assessments for all scheduled visits. Subjects who prematurely discontinue study drug treatment will complete a Safety Follow-up Visit.

Figure 6-1 Study Design

- All subjects start treatment with lumacaftor/ivacaftor on Day 1.
- Safety Follow-up visit is required only for subjects who do not begin commercially available LUM/IVA within 28 (\pm 7) days of last dose of study drug.

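### The SAP's definition of study completion requires a follow-up visit that subjects starting commercial LUM/IVA are excused from, so such subjects are not counted as completers

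*SAP*

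**What the plan says.** SAP 8.2.1 (Subject Disposition) reports numbers and percentages of the Full Analysis Set (FAS), overall and by arm. Three of its categories matter here:

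- "Completed study drug", which does not mention the follow-up visit;
- "Completed study (defined as completed the planned study treatment and Safety Follow-up Visit"), which joins two conditions and states no exception;
- "Prematurely discontinued the study and the reason for discontinuation", which is not defined further.

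It also calls for a listing, with reasons, of subjects who discontinued treatment or study.

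The follow-up visit is not universal. Protocol 8.1.3 says: "Subjects who begin commercial LUM/IVA before this visit do not have to complete the Safety Follow-up Visit". SAP Section 6 says that subjects who begin commercial therapy within 28 (± 7) days of last dose "do not have to complete the Safety Follow-up Visit", and the notes to its Figure 6-1 repeat this: "Safety Follow-up visit is required only for subjects who do not begin commercially available LUM/IVA within 28" (± 7) days. Protocol 13.1.1.3 plans for the resulting group with its own adverse-event cut-off, beginning "For enrolled subjects who do not have a Safety Follow-up Visit".

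The protocol's own disposition paragraph (12.3.2.1) gives only the label "completed study/Safety Follow-up Visit" and does not mention the waiver.

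**The concern.** The completion definition and the waiver do not fit together. A subject can meet every requirement of the protocol, including proper use of the waiver, and still fail the SAP's test for completing the study. LUM/IVA was already approved in several regions for this genotype (protocol 5.1), and the protocol makes explicit provision for subjects who move to commercial supply, so the case is a foreseen one.

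At stake is one reported percentage, shown overall and by arm. Readers use the disposition table to judge how many subjects saw the study through. All planned comparative analyses have been dropped (SAP Sections 3 and 5.1), so the report is descriptive and its simple counts should be right.

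**Working it through.** Neither document gives a completion rate or a rate of transfer to commercial drug, so there is no plan figure on this point to reproduce. The sample-size statement does not enter the argument.

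**Step 1: apply the rules to one subject.** Take a subject who finishes planned treatment, starts commercial LUM/IVA within the waiver, and does not attend the follow-up visit.

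| SAP 8.2.1 category | Result |
|---|---|
| Completed study drug | Yes |
| Prematurely discontinued study drug | No |
| Completed study | No: the visit condition is not met |
| Prematurely discontinued the study | Not determined by the text |

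No section of either document says that a waived visit counts as completed.

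**Step 2: effect on the reported percentage.** Let

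- c = share of the FAS completing planned treatment (not in the documents; assumed);
- s = share of those treatment completers who are excused and have no visit (not in the documents; assumed).

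If every required visit is done:

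- reported study completion = c × (1 − s);
- study completion with the waiver respected = c;
- shortfall = c − c × (1 − s) = c × s, which cannot exceed c.

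For example, with an FAS of 75 (the planned number), c = 80% and s = 0.5, there are 75 × 0.80 = 60 treatment completers. The row would count 60 × (1 − 0.5) = 30, or 30/75 = 40%, instead of 80%.

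Reported study completion (%) over a range of assumptions:

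| c | s = 0 | s = 0.25 | s = 0.5 | s = 0.75 | s = 0.9 | s = 1 |
|---|---|---|---|---|---|---|
| 100% | 100 | 75 | 50 | 25 | 10 | 0 |
| 80% | 80 | 60 | 40 | 20 | 8 | 0 |
| 50% | 50 | 37.5 | 25 | 12.5 | 5 | 0 |

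In every cell the treatment-completion row stays at c.

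**Step 3: where the excused subjects go.** The SAP leaves two possibilities. If they are classed as prematurely discontinued, that row rises by c × s and the listing needs a reason that does not exist. If they are in neither category, the two study-level rows fall short of the FAS by c × s. The programmer has no rule for choosing.

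**Step 4: compare the waiver wordings.** Protocol 8.1.3 turns on whether commercial drug was begun before the visit. Protocol 8.1 states no time limit. The note to protocol Figure 8-1, and SAP Section 6, use a window of 28 (± 7) days from last dose. These can differ: a subject who starts commercial drug after the date on which the visit was due, but still inside the window, is excused under the window and not under 8.1.3.

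**The case against.** The strongest reply is that this is a loose phrase in one descriptive row, and much of that reply stands.

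- **Discontinuation.** A reader might infer that excused subjects are reported as premature discontinuations, so that attrition is overstated. The SAP does not say so. It lists the two study-level categories separately, does not define the second as everyone outside the first, and leaves it otherwise undefined. The text supports an undercount of completers and no more. The eCRF, which might settle the classification, is not among the documents.
- **Persistence.** A reader might infer that a central result of an adherence trial is distorted. It is not. Completion and discontinuation of study drug have their own rows, exposure is summarised by duration (SAP 8.2.5), the adherence endpoints use bottle openings over eligible treatment duration (SAP 8.3.2), and safety uses the Safety Set (SAP 8.4). None of these uses study-completion status.
- **Size.** A reader might suppose that most completers move to commercial drug. The documents allow for that route but do not say how often it is taken.
- **Early termination.** SAP Section 3 says the study stopped early with limited data. Only subjects who finished the planned treatment can be affected, and that may be few.

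What the reply does not remove is the conflict itself. The definition carries no qualifier, and the protocol's label in 12.3.2.1 does not supply one.

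**Conclusion.** The point holds as a minor error in a descriptive definition. As written, SAP 8.2.1 fails to count as study completers those who finished planned treatment and were properly excused from the follow-up visit, and it does not say where they belong instead.

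The undercount is c × s of the FAS, on the assumption that all required visits take place. Since c and s are unknown, the documents fix only the limits: no effect if nobody is excused, and no counted completers if every treatment completer is. Early termination probably keeps c low, which caps the absolute effect, but the documents give no count. The documents do not support a claim that discontinuation is overstated or that persistence on drug is misreported.

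**What to change.** In SAP 8.2.1:

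1. Define study completion as completing planned study treatment and the Safety Follow-up Visit where that visit is required, and state that a subject excused because commercial LUM/IVA was begun counts as having completed.
2. State that such subjects are not classed as prematurely discontinued from the study.

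The definition should point to the waiver and not restate a time window, because protocol 8.1.3 and SAP Section 6 word the waiver differently. Those passages should be reconciled; which wording governs is for the sponsor to decide.

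With this change the row equals c when all required visits are done. The cost is a sentence or two in the SAP and a small change to the disposition program. It needs a record of when commercial drug was started. That is likely to exist, because protocol 9.3.1 records concomitant medication and 13.1.1.3 uses commercial dosing as an adverse-event cut-off, but it should be checked against the eCRF. No visit, clinical rule, sample size or other analysis changes.

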8.2.2 Demographics and Baseline Characteristics

Demographics, medical history and baseline characteristics will be summarized overall and by study arm based on the FAS.

Demographic data will include the following:

- Age at screening (in years)
- Age group at screening (≥ 16 to < 23 , and ≥ 23 years)
- Sex (female and male)
- Ethnicity (Hispanic or Latino, not Hispanic or Latino, and not collected per local regulations)
- Race (White, Black or African American, Asian, American Indian or Alaska Native, Native Hawaiian, Other Pacific Islander, and Other)

Baseline characteristics will include the following:

- Weight (kg) at study baseline
- Height (cm) at study baseline
- BMI (kg/m^2) at study baseline

Other baseline characteristics will include the following:

- Percent predicted FEV₁ at screening
- Percent predicted FEV₁ severity ($< 70\%$ versus $\geq 70\%$ predicted) at screening

No statistical tests will be carried out to evaluate any imbalance at enrollment between study arms.

Medical history will be summarized by MedDRA system organ class (SOC) and preferred term (PT).

8.2.3 Medical History

Medical history will be coded by using the Medical Dictionary for Regulatory Activities (MedDRA). Medical history will be summarized descriptively by system organ class (SOC) and preferred term (PT) overall and by study arm based on the FAS. It will also be listed.

8.2.4 Prior and Concomitant Medications

Medications used in this study will be coded by using the World Health Organization Drug Dictionary Enhanced (WHODDE) and categorized as the following:

Prior medication: any medication that started before the first dose date of study drug, regardless of when the medication ended.

Concomitant medication: medication continued or newly received during the TE period.

Post-treatment medication: medication continued or newly received after the TE period.

A given medication may be classified as follows: prior, concomitant, post-treatment, both prior and concomitant, both concomitant and post-treatment, or prior, concomitant, and post-treatment.

For medications with partial start dates, missing month will be imputed with January and missing day will be imputed with 1. For medications with partial stop dates, missing month will be imputed with December and missing day will be imputed with the last day of the month. Details for imputing missing or partial start and/or stop dates of medication are described in [Appendix C](#).

If a medication has a completely missing or partially missing start/stop date and it cannot be determined whether it was taken before the first dose date, concomitantly, or after the TE period, it will be classified as prior, concomitant, and post-treatment.

The logic to decide the category of a medication is presented in Table 8-1:

Table 8-1 Logic for Determining the Category of a Medication

Medication start date	Medication end date		
	< first dose date of study drug	≥ first dose date and ≤ End date of TE period	> End date of TE period
< first dose date of study drug	P	PC	PCA
≥ first dose date and ≤ End date of TE period	-	C	CA
> End date of TE period	-	-	A

P: Prior; C: Concomitant; A: Post-treatment

Summaries of prior and concomitant medications will be based on the FAS. They will also be listed by subject.

8.2.5 Study Drug Exposure

Exposure summaries will be based on the FAS and presented by treatment group.

Duration of study drug exposure is defined as follows: last dose date – first dose date + 1 day within the treatment period, regardless of any interruption in dosing between the first and the last dose.

If the last dose date of study drug is missing, the subject's discontinuation or completion date will be used for analysis purposes.

Exposure will be summarized as a continuous variable in weeks, and also in the following categories: ≤ 6 weeks, >6 and ≤ 12 weeks; >12 and ≤ 24 weeks; >24 and ≤ 36 weeks; >36 and ≤ 48 weeks; and >48 weeks, for each treatment group.

8.2.6 Study Drug Compliance

Study drug compliance based on number of tablets will be assessed by calculating the percentage of tablets consumed relative to the expected number of tablets administered during the subject's actual time on-study. The expected number of tablets administered during the subject's actual time on-study will be 4 tablets per day multiply the number of days in the study. The number of tablets consumed is the difference between the expected number of tablets dispensed and the total number of tablets returned.

These pharmacy and subject reported compliance data will be summarized during the overall treatment duration (from first dose to last dose), based on the medication interruption days.

Compliance rate based on the interruption days will be calculated as follow:

$$100 \times [1 - (\text{total number of days of any study drug interruption}) / (\text{duration of study drug exposure})]$$

The total number of days study drug interrupted is defined as the total of number of days the study drug was interrupted in each interruption interval, where number of days study drug interrupted in each interval is defined as the interruption end date - the corresponding interruption start date + 1.

Study drug compliance will be summarized descriptively by the number of subjects (n), mean, SD, median, min, and max. They will also be summarized in categories: $<80\%$ and $\geq 80\%$ using frequency tables.

Study drug compliance summaries will be based on the FAS.

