#### **12.3.2.4    Study Drug Exposure and Compliance**

Exposure to LUM/IVA (i.e., duration of treatment in days) will be summarized for the FAS in terms of duration of treatment a subject received (in days), defined as the last day minus the first day of LUM/IVA plus 1. Exposure will be summarized by study arms for the FAS.

Primary and secondary analyses of adherence will be performed through smart technology generated data. A complementary analysis based on pill count and missing/interruption of dose

will be conducted. Information on number of pills and drug interruption will be collected from dispensing pharmacy and subjects.

These pharmacy and subject reported compliance data will be summarized for the FAS and will be derived in at least 1 of 2 methods pending data availability:

(1) based on pill counts calculated as:

$$100 \times (\text{total number of tablets taken}) / (4 \times \text{duration of LUM/IVA exposure in days})$$

And/or:

(2) based on medication interruption days using the formula:

$$100 \times [1 - (\text{total number of days LUM/IVA interrupted} \geq 72) / (\text{duration of LUM/IVA exposure})]$$

Duration of treatment and dosing compliance will be summarized by means of descriptive summary statistics.

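### SAP 8.2.6 bases pill-count compliance on undefined days in the study, where the protocol uses duration of exposure; read literally, this understates compliance

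*SAP*

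**What the plan says.** Protocol 12.3.2.4 defines pill-count compliance as 100 times tablets taken, divided by 4 times the "duration of LUM/IVA exposure in days". It defines exposure as the last day minus the first day of LUM/IVA, plus 1.

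SAP 8.2.6 describes the same measure as "the percentage of tablets consumed relative to the expected number of tablets administered" over the subject's time on study. It then sets the expected number at "4 tablets per day multiply the number of days in the study". Neither expression for the period is given a start or an end date.

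The second rate in SAP 8.2.6, based on interruption days, divides by duration of study drug exposure. SAP 8.2.5 defines that as last dose date minus first dose date plus 1 day, "within the treatment period, regardless of any interruption in dosing between the first and the last dose".

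SAP 8.2.6 also says: "These pharmacy and subject reported compliance data will be summarized during the overall treatment duration (from first dose to last dose"; the sentence then closes by tying the summary to interruption days. Both compliance measures are to be tabulated as below 80% versus 80% or more.

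**The concern.** The SAP and the protocol state different denominators for one measure, and the two rates in SAP 8.2.6 may run over different periods for the same subject. SAP Section 3 explains that the planned analyses were cut back because of early termination, but nothing there accounts for a new pill-count denominator.

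The difference matters because the study contains days on which no tablets are due. SAP Section 6 lists Screening and a Safety Follow-up Visit 28 (±7) days after the final dose as parts of the study, separate from the Treatment Period. Counting such days raises the expected number of tablets and leaves the number consumed unchanged, so compliance can only be understated. The shortfall is largest, in relative terms, for subjects with short exposure. Those are to be expected in a study that stopped early, and the exposure categories in SAP 8.2.5 start at 6 weeks or less. Two programmers could both follow SAP 8.2.6 and report different percentages for the same subject.

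**Working it through.** The plan gives no numerical result for compliance, so there is no figure to reproduce. The check compares the two stated rules for one hypothetical subject.

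**Inputs**
- Tablets due per day: 4 (Protocol 12.3.2.4; SAP 8.2.6).
- D = days of exposure. D = 84 is 12 weeks, D = 168 is 24 weeks and D = 336 is the full 48 weeks.
- F = off-drug days counted as days in the study. The follow-up window of 28 (±7) days gives F = 21, 28 or 35. That these days are counted at all is an assumption.
- Cut-off: 80% (SAP 8.2.6).

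**Protocol rule.** A subject who takes every tablet consumes 4D. The rate is 100 × 4D / (4 × D) = 100% for any D.

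**SAP rule read literally, with F off-drug days.** The rate is 100 × 4D / [4 × (D + F)] = 100 × D / (D + F).

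| D (days) | F = 0 | F = 21 | F = 28 | F = 35 |
|---|---|---|---|---|
| 84 | 100% | 84/105 = 80.0% | 84/112 = 75.0% | 84/119 = 70.6% |
| 168 | 100% | 168/189 = 88.9% | 168/196 = 85.7% | 168/203 = 82.8% |
| 336 | 100% | 336/357 = 94.1% | 336/364 = 92.3% | 336/371 = 90.6% |

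**When a fully compliant subject drops below 80%.** 100 × D / (D + F) < 80 means 0.2D < 0.8F, so D < 4F. The limits are D < 84 for F = 21, D < 112 for F = 28 and D < 140 for F = 35. At D = 84 with F = 21 the score is exactly 80.0%, which still counts as 80% or more.

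Screening days, if counted, would enter the formula in the same way. The table leaves them out, so it shows one possible reading and not the full literal one.

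**The case against.** The best reply is that this is loose wording and that on-treatment days were always meant. There is good support for it:

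- The SAP speaks of tablets expected to be administered, at 4 per day, which makes sense only on dosing days.
- Exposure is defined in the section immediately before.
- Drug counts are scheduled at Weeks 12, 24, 36 and 48, with none at the Safety Follow-up Visit (Protocol Table 3-2).
- The protocol uses the same opening words for both compliance methods: "These pharmacy and subject reported compliance data will be summarized for the FAS". The SAP attaches those words to the span from first to last dose.
- Read literally, the rule would also count Screening, which nobody is likely to have wanted.

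This makes the intention probable, and it stands to that extent. It does not settle the rule. The first-to-last-dose sentence ends by referring to interruption days, so it can be read as governing only the other rate. The pill-count sentence still names a different and undefined period.

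Three limits also stand. Subjects who begin commercial LUM/IVA need not attend the follow-up visit (Protocol 8.1.3). The protocol promises only at least one of its two compliance methods, depending on data availability. And the documents do not say how many subjects had short exposure or a follow-up visit.

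A reader might go further and infer that exposure itself is unsound, because SAP 8.2.5 replaces a missing last dose date with the subject's "discontinuation or completion date will be used for analysis purposes" and does not say whether that date refers to study drug or to the study. The documents do not support making much of this. It arises only when the last dose date is missing, and 8.2.5 confines exposure to the treatment period, which SAP Section 6 lists separately from Safety Follow-up. SAP 8.2.1 also reads "Completed study (defined as completed the planned study treatment and Safety Follow-up Visit", so a study completion date requires the planned treatment to have been completed and would not apply to a subject who stopped early. It is a small ambiguity worth a clarifying word.

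**Conclusion.** The inconsistency is real. The pill-count denominator written in SAP 8.2.6 departs from the protocol and from the other rate in the same section, and applied literally it gives compliance that is too low. In the illustration, a subject with perfect intake over 84 days scores 70.6% to 80.0% instead of 100%; over the full 336 days the score is 90.6% to 94.1%. These figures assume that the whole follow-up interval of 21 to 35 days is counted. They do not estimate what happened in the trial, and if only on-treatment days are used the effect is zero.

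A reader might infer that compliant subjects will in fact be misclassified, or that the adherence results are compromised. Neither follows. The documents do not show that any off-drug day would be counted. The smart-bottle endpoints in SAP 8.3.2 have their own denominator, based on eligible treatment duration or a fixed 84 days. The compliance table is descriptive and supportive, and no test rests on it. This is a correction worth making, of low severity.

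**What to change.** In SAP 8.2.6, replace "4 tablets per day multiply the number of days in the study" with 4 times the duration of study drug exposure in days (Section 8.2.5), and describe the period as exposure instead of time on study. This matches Protocol 12.3.2.4 and puts both compliance rates on the same period. No change to the numerator is proposed.

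As a minor addition, state in SAP 8.2.5 that the date substituted for a missing last dose date is the study drug discontinuation or completion date.

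The cost is SAP wording only. Exposure is already derived under SAP 8.2.5, and study drug completion and discontinuation are already reported under SAP 8.2.1, so no new data are needed.
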